## **INTRODUCTION**

This document is a protocol for a human research study. This study is to be conducted according to US and international standards of Good Clinical Practice (FDA Title 21 part 312 and International Conference on Harmonization guidelines), applicable government regulations and Columbia University Medical Center institutional research policies and procedures.

Prostate cancer is a major contributor to cancer morbidity and mortality in men (Jemal A et al, 2017). Treatment of localized disease typically involves either surgery or radiation. However, a significant number of men treated with definitive local therapy will eventually have PSA recurrence and develop clinical metastases (Roehl KA et al, 2004). Although some patients will demonstrate clear metastatic disease on imaging, a significant number of men will only have biochemical recurrence (BCR) with a rising PSA (Freedland SJ et al 2005).

Androgen deprivation therapy (ADT) can lead to rapid disease control for men with metastatic or non-metastatic hormone-sensitive prostate cancer. However, ADT is associated with significant side effects including decreased libido, increased fat mass, insulin resistance and osteoporosis (Litwin MS et al, 2017). Intermittent ADT (IADT) which has been shown to be non-inferior to continuous ADT allows for reduced ADT exposure (Crook JM et al 2012; Magnan S et al 2015; Klotz L et al 2017). However, the ADT free interval typically decreases with each cycle of IADT and all men will eventually progress to a castration-resistant state (Crook JM et al 2012). Therefore, developing novel strategies to prolong the ADT free interval and allow for recovery of testosterone while maintaining adequate disease control are essential to improving outcomes for prostate cancer patients.

Immunotherapy has shown mixed efficacy in prostate cancer to date. Although Sipuleucel T (Sip-T), an autologous cancer vaccine, can improve overall survival in castration-resistant prostate cancer (CRPC), other immunotherapy approaches like checkpoint blockade have been relatively unsuccessful when tested in patients with CRPC. However, it is becoming increasingly clear that the immune tumor microenvironment changes dramatically during disease progression and in response to ADT. For example initially ADT induces thymic output of T-cells with subsequent tumor infiltration ([name] CG et al, 2005). However, with prolonged ADT and disease progression a more immunosuppressive tumor microenvironment develops with increased regulatory T cells (Tregs) and myeloid-derived suppressor cells (MDSCs) ([name] et al, 2005; Gannon PO et al, 2009). Recent data from Antonarakis et al also demonstrated that sequencing immunotherapy with Sipuleucel-T prior to ADT elicits a more robust immune response than ADT followed by Sipuleucel-T (Antonarakis et al, 2017). However, whether checkpoint blockade in combination with standard ADT can lead to more effective disease control and less exposure to ADT exposure for patients with less advanced hormone-sensitive disease remains unknown. In addition, data from our group and others have identified infiltration of PMN-MDSCs through increased production of IL-8 as an important mechanism of immune resistance in prostate cancer. In particular, pre-clinical data demonstrate a process by which ADT leads to secretion of IL-8 and attraction of PMN-MDSCs, thereby promoting immune resistance (Gannon PO et al, 2010; [name] lab unpublished data). Therefore, adding IL-8 targeted therapy to checkpoint blockade and ADT could further enhance anti-tumor immunity and offer patients with prostate cancer the potential to develop durable immune responses.

This is a two-arm, multicenter, phase 1b/2 study to assess the efficacy of immunotherapy with either Nivolumab (anti-PD-1) or Nivolumab plus BMS-986253 combined with ADT using Degarelix (LHRH antagonist) for men with hormone-sensitive prostate cancer and a rising PSA (30 patients per group), with a primary endpoint of rate of PSA recurrence 12 months after completion of therapy. We hypothesize that immunotherapy with either Nivolumab alone or Nivolumab plus BMS-986253 combined with Degarelix will decrease the percentage of men with hormonse-sensitive prostate cancer and a rising PSA who have PSA recurrence 12 months after completion of therapy from 50% (historical reference; McKay RR et al, 2016) to 25%. Baseline and on-treatment biopsies will be obtained for a subgroup of patients with biopsy accessible lesions in each group to characterize the immune effects of therapy.

# **STUDY OBJECTIVES**

## Primary Objective

- Determine the rate of PSA recurrence defined as a PSA >0.2ng/ml for radical prostatectomy patients or PSA >2.0ng/ml for patients who received other primary therapies (e.g. radiation, cryotherapy, brachytherapy) at a time point of 10 months after start of therapy.
- Determine the safety and tolerability of either nivolumab or nivolumab plus BMS-986253 in combination with degarelix in men with hormone-sensitive prostate cancer.

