# **STUDY DESIGN**

# General Design

This is a multi-center, two-arm, open-label, phase 1b/2 study evaluating the anti-tumor effect of either Nivolumab alone or Nivolumab plus BMS-986253 with androgen deprivation therapy using Degarelix in men with hormone-sensitive prostate cancer and a rising PSA. Patients will be recruited from outpatient clinics at participating sites and randomized to either Nivolumab alone (Arm A) or Nivolumab plus BMS-986253 (Arm B).

**Study Interventions:** Eligible patients in Arm A will receive Nivolumab every 4 weeks for 2 doses and then Nivolumab + Degarelix every 4 weeks x 4 doses. Eligible patients in Arm B will receive Nivolumab every 4 weeks x2 doses + BMS-986253 every 2 weeks x 4 doses and then

Nivolumab every 4 weeks x 4 doses + BMS-986253 every 2 weeks x 8 doses + Degarelix every 4 weeks x 4 doses.

Schedule of Evaluations: During treatment patients will have safety assessments including routine bloodwork and physical examinations at each visit. (See Section 12 for detailed study evaluations and the study schedule). Safety evaluations will also occur until 100 days after the last treatment doses.

The primary endpoint will be evaluated by assessing the PSA 10 months after start of therapy. PSA and serum testosterone will be checked monthly during treatment (+/- 3 days), the end of treatment visit (+/- 1 week), every 2 months (+/- 1 week) or until progression of disease during year 1 of follow up and every 3 months (+/- 1 month) or until progression of disease during year 2 of follow up. Sera, whole blood and CBC with differential will be collected for immunoassays at initiation of immunotherapy, at initiation of degarelix, end of treatment visit and 10, 14 and 18 month (+/- 1 week). Patients will also have CT or MRI scans (chest, abdomen and pelvis) and bone scan at screening, end of treatment and 10 months after start of therapy. Toxicity evaluation will utilize CTCAE v5.0 criteria.

**Duration of Treatment:** Subjects will receive treatment for a total of 6 months or intolerable toxicity or side effects.

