#### STATISTICAL CONSIDERATIONS

#### Study Design and Sample Size

This is a multicenter, 2-arm phase 1b/2 trial to evaluate the activity of Nivolumab or Nivolumab plus BMS-986253 with IADT using Degarelix in men with hormone sensitive prostate cancer with a rising PSA. The primary endpoints of this trial is rate of PSA recurrence 10 months after start of therapy. Within the context of this proposed trial, we will target a decrease in post-therapy PSA recurrence at 10 months of 25% compared to a historical recurrence rate of 50% with intermittent ADT alone. Probabilities of type I and type II error will be set at 0.05 and 0.2 respectively. The study will include a total of 23 evaluable patients per arm. This study design yields at least 80% power to detect a PSA recurrence rate of 25% at 10 months after start of therapy (compared to the null hypothesis of 50%) at a significance level of 5%. Accounting for a dropout rate of 20%, we will plan to enroll a total of 30 patients per arm.

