#### Study Endpoints

We will use one-sided binomial tests to compare the post-therapy PSA recurrence rate in each arm with the historical recurrence rate of 50%. To compare the secondary outcomes between the two arms, Kaplan-Meier estimators and log-rank tests will be used to compare time-to-event variables (e.g., time to PSA recurrence, time to recovery of testosterone, and time to next anti-cancer treatment); Chi-squared tests will be used to compare incidence rates (e.g., incidence of metastases); t-tests will be used to compare continuous measurements (e.g., changes immune cell density and proximity). We will set the nominal significance level at 5%. Only patients undergoing randomization to the treatment arms will be used for comparison between the treatment arms.

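### The PSA recurrence cut-off differs tenfold by primary therapy, yet each arm is tested against one fixed 50% and no stratification by primary therapy is described

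*Combined protocol and SAP*

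**What the plan says.** The Primary Objective sets recurrence at "PSA >0.2ng/ml for radical prostatectomy patients or PSA >2.0ng/ml for patients who received other primary therapies", assessed "at a time point of 10 months after start of therapy". The Secondary Objectives and the Biochemical Response/Progression section use the same two cut-offs.

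Study Endpoints states: "We will use one-sided binomial tests to compare the post-therapy PSA recurrence rate in each arm with the historical recurrence rate of 50" per cent. Study Design and Sample Size builds the trial on that rate: "Probabilities of type I and type II error will be set at 0.05 and 0.2 respectively". It plans for 23 evaluable men in each arm and claims power of 80% or more if the true month-10 rate is 25%. The Introduction takes the 50% from one cited trial of short-course ADT. It gives neither that trial's prostatectomy share nor its rate by primary therapy.

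Under General Design, patients are "randomized to either Nivolumab alone (Arm A) or Nivolumab plus BMS-986253 (Arm B"), with no stratification factor named. Study Endpoints compares the arms by Kaplan-Meier and log-rank methods for time-to-event outcomes, including time to PSA recurrence. It mentions no stratification, covariate or subgroup for primary therapy.

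**The concern.** A man treated by prostatectomy counts as recurred at a tenth of the PSA required of any other man. An arm's month-10 rate is therefore an average over two differently defined events, weighted by the prostatectomy share. The null is one number that does not move with that share.

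If the enrolled mix has a true ADT-alone rate below 50%, an arm can beat the benchmark too easily with no immunotherapy effect. If the rate is above 50%, a real effect can be missed. Separately, without stratified allocation the two arms can differ by chance in a factor that helps determine the endpoint, which adds noise to the comparison of time to PSA recurrence.

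**Working it through.** **Inputs from the documents.** Cut-offs 0.2 and 2.0 ng/ml; null 50%; target 25%; one-sided 5%; 23 evaluable and about 30 enrolled per arm.

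**1. The plan's own figure.** Let X be the number of recurrences, X ~ Binomial(23, p), and reject when X ≤ 7.
- P(X ≤ 7 | p = 0.50) = 0.0466, below 0.05. The next cut-off, 8, would exceed 0.05.
- P(X ≤ 7 | p = 0.25) = 0.8037, so power is at least 80%.

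The stated sample size is reproduced. The arithmetic is sound; the question is what the 50% represents.

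**2. How the null depends on the mix.** With prostatectomy share s and ADT-alone month-10 rates a (prostatectomy) and b (other), the arm's true null is p0 = s·a + (1 − s)·b. This is free of s only if a = b. The cut-off ratio is 2.0/0.2 = 10, or log2(10) = 3.32 doublings, so equality would need an offsetting difference in starting PSA or PSA kinetics. The documents report neither a nor b.

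**3. Sensitivity of the test.** Same rule, P(X ≤ 7 | p0):

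| True ADT-alone rate in the enrolled mix | False-positive rate |
|---|---|
| 40% | 23.7% |
| 45% | 11.5% |
| 50% | 4.7% |
| 55% | 1.5% |

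**4. From share to null.** The group rates below are assumptions, each pair averaging 50% at a 50% prostatectomy share. Power is for a treatment that halves p0.

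| Assumed a / b | Share s | p0 | False-positive rate | Power |
|---|---|---|---|---|
| 55% / 45% | 30% | 0.3×55 + 0.7×45 = 48% | 6.9% | 83% |
| 55% / 45% | 70% | 0.7×55 + 0.3×45 = 52% | 3.1% | 77% |
| 60% / 40% | 30% | 0.3×60 + 0.7×40 = 46% | 9.8% | 86% |
| 60% / 40% | 70% | 0.7×60 + 0.3×40 = 54% | 2.0% | 73% |
| 65% / 35% | 30% | 0.3×65 + 0.7×35 = 44% | 13.5% | 89% |
| 65% / 35% | 70% | 0.7×65 + 0.3×35 = 56% | 1.2% | 70% |

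**5. Chance imbalance between arms.** With 30 per arm and unstratified allocation, the two prostatectomy shares are independent Binomial(30, s)/30. They differ by 20 points or more with probability about 15% at s = 50% and 12% at s = 70%.

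**6. The log-rank test.** In simulations with no treatment effect and assumed group rates of 65% and 20%, type I error was 5.2% to 5.9% unstratified and 5.8% stratified, so both are close to nominal. With an assumed hazard ratio of 0.45, stratifying raised power from about 50% to 71%. The two groups differ widely in that example, and the gain shrinks as their rates come closer.

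**The case against.** **The cut-offs may offset each other.** A reader might infer that men without prostatectomy can rarely reach 2.0 ng/ml by month 10, so that the rate mostly measures the prostatectomy share. The argument would run as follows. Six 28-day cycles end near day 169 and month 10 is near day 304, leaving (304 − 169)/30.44 = 4.43 months. From 0.05 ng/ml, crossing 0.2 needs a doubling time under 4.43/2 = 2.2 months, and crossing 2.0 needs one under 4.43/5.32 = 0.8 months.

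That gives both groups the same PSA after ADT, which no section states. Men who kept their prostate may start higher. From 0.5 to 2.0 is two doublings, exactly as from 0.05 to 0.2, and the gap disappears. The Radiographic Progression section also provides for men with metastatic disease at baseline, whose PSA need not start low. This objection stands, and the stronger reading is not supported.

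**The reference may already be mixed.** The title of the cited trial refers to recurrence after definitive local therapy. If its mix and definition resemble this trial's, the bias is small. That is possible, but the documents do not let a reader check it.

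**Randomisation protects the between-arm test.** This stands too. Chance imbalance is already covered by the 5% level, so the unstratified log-rank test is valid and stratifying gains precision only. Nor does stratified randomisation do anything for the tests of each arm against 50%.

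**The text may be incomplete.** No detailed randomisation section is available here, so the most that can be said is that no stratification factor is described.

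**Conclusion.** The point holds as a dependence that the plan leaves uncontrolled, not as a demonstrated bias. Three facts come straight from the document: the tenfold difference in cut-off, the single fixed 50% for each arm, and no described stratification or analysis by primary therapy. That each arm's null depends on its mix follows unless the two groups have equal month-10 rates.

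The size and direction cannot be fixed from the documents. Under assumed rates of 60% and 40%, prostatectomy shares of 30% and 70% give false-positive rates of 9.8% and 2.0%, against a planned 4.7%. With a gap of only 10 points the effect is minor (6.9% and 3.1%). These figures assume that the reference rate of 50% corresponds to an even mix, which is itself unknown.

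The benchmark has two related loose ends. The Introduction ties the 50% to 12 months after completing therapy, whereas the test is at 10 months from the start. The Biochemical Response/Progression section also requires two serial rises, which the Primary Objective does not. Both need to be reconciled before the 50% can be matched to any mix.

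**What to change.** **Between-arm comparison.** Stratify randomisation by primary local therapy (prostatectomy or other), and use a log-rank test stratified by the same factor for time to PSA recurrence. If randomisation is already complete, the stratified analysis is still available.

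**Primary endpoint.**
- Keep the one-sided binomial test against 50%.
- Report month-10 rates by cut-off group within each arm.
- State the reference study's prostatectomy share and its recurrence definition.
- If that study gives rates by primary therapy, repeat the test as a sensitivity analysis with p0 = s·a + (1 − s)·b, where s is the enrolled prostatectomy share.

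**Cost.** One stratification factor, which must be recorded anyway to score the endpoint, one table and one extra test. The subgroup rates will be imprecise with 23 evaluable men per arm, and the re-weighted null may be less favourable than 50%. If the reference gives no rates by primary therapy, the re-weighted test cannot be done, and the report should say so.

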#### Secondary Objectives

- To assess the relapse-free survival (RFS) after recovery of testosterone with relapse defined as a PSA >0.2ng/ml for radical prostatectomy patients or PSA >2.0ng/ml for patients who received other primary therapies and recovery of testosterone defined as a testosterone (>150ng/dl).
- Determine the % change in PSA to immunotherapy by comparing the PSA prior to and following 8 weeks of immunotherapy and before initiation of ADT.

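### The raw 8-week PSA change mixes natural PSA growth with drug effect within each arm; compare arms on log PSA adjusted for pre-study slope, and keep the within-arm figure descriptive

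*Combined protocol and SAP*

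**What the plan says.** Under Secondary Objectives the protocol sets out to "Determine the % change in PSA to immunotherapy by comparing the PSA prior to and following 8 weeks of immunotherapy", with the second value taken before ADT starts. General Design describes the population as "in men with hormone-sensitive prostate cancer and a rising PSA".

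Patients are "randomized to either Nivolumab alone (Arm A) or Nivolumab plus BMS-986253 (Arm B"). In the period before degarelix, "Arm A will receive Nivolumab every 4 weeks for 2 doses and then Nivolumab + Degarelix", while "Arm B will receive Nivolumab every 4 weeks x2 doses + BMS-986253 every 2 weeks x 4 doses". Nivolumab is therefore given in both arms, and the arms differ only by BMS-986253. PSA is measured monthly during treatment.

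For secondary outcomes, Study Endpoints plans comparisons between the two arms. For continuous outcomes it says "t-tests will be used to compare continuous measurements (e.g., changes immune cell density and proximity"). The PSA change is not named, but the list is given as examples, so the outcome reasonably belongs to that class.

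The text gives no pre-treatment slope, doubling time, reference value, response threshold or growth adjustment for this outcome.

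**The concern.** The objective words the before/after change as the change due to immunotherapy. That reading would be natural if PSA were expected to stay level without treatment. In men selected because PSA is rising, the no-effect value is a rise, and its size differs from man to man with his doubling time. The arm-level figure then reflects the mix of doubling times enrolled as well as any drug effect.

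Among the stated objectives, this is the only clinical efficacy measure taken before degarelix. The 10-month recurrence rate and the relapse-free survival after testosterone recovery both follow ADT. If the 8-week figure is reported alone, the lead-in gives little interpretable clinical information on nivolumab without ADT, and a modest slowing of PSA growth would go unrecognised.

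**Working it through.** **Plan's own figures.** The plan states no sample size, SD or power for this outcome, so there is no figure to reproduce for it. The primary design does reproduce. With 23 evaluable men and success declared at 7 or fewer recurrences, the exact one-sided type I error against 50% is 0.0466 and the power at 25% is 0.8037. Nothing below touches that.

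**Inputs.** From the documents: 8 weeks (56 days) of immunotherapy before ADT, and 30 men enrolled per arm. Assumed: exponential PSA growth, pre-treatment doubling times (DT) of 3 to 12 months, and SDs of the log-PSA change of 0.15 and 0.3.

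**Step 1: expected change with no drug effect.** 56 / 30.44 = 1.84 months. Percent change = 2^(1.84/DT) − 1. Halving the growth rate replaces DT by 2 × DT.

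| Assumed DT (months) | No drug effect | Growth rate halved |
|---|---|---|
| 3 | +53.0% | +23.7% |
| 6 | +23.7% | +11.2% |
| 9 | +15.2% | +7.3% |
| 12 | +11.2% | +5.5% |

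Every entry is a rise. A man slowed from a 3-month to a 6-month doubling time reads +23.7%, the same as an unaffected man whose doubling time was 6 months all along.

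**Step 2: dependence on case mix.** With no drug effect, an arm made up half of 3-month and half of 12-month men averages (53.0 + 11.2)/2 = +32.1%. With one quarter 3-month men the average is 0.25 × 53.0 + 0.75 × 11.2 = about +22%. The figure moves by about 10 percentage points with no change in the drug.

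**Step 3: what the randomised comparison can do.** Average natural growth cancels in B minus A. Halved growth in B relative to A is a log-PSA difference of 0.5 × ln 2 × 1.84/DT, which is 0.213, 0.106, 0.071 and 0.053 at DT 3, 6, 9 and 12. With 30 per arm and a two-sided 5% level, power = Φ(difference / (SD × √(2/30)) − 1.96):

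| Assumed DT (months) | SD 0.15 | SD 0.3 |
|---|---|---|
| 3 | about 100% | 78% |
| 6 | 78% | 28% |
| 9 | 45% | 15% |
| 12 | 28% | 10% |

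**Step 4: noise from unadjusted growth.** In the half-and-half mix, the no-effect log changes are ln 2 × 1.84/3 = 0.425 and ln 2 × 1.84/12 = 0.106. Their SD is (0.425 − 0.106)/2 = 0.16. If the total SD is 0.3 and a covariate removed all of this part, the residual SD would be √(0.09 − 0.0256) = 0.25. For a difference of 0.106, power would rise from 28% to about 37%. That is a ceiling, because an estimated slope removes only part of the growth variance.

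**The case against.** The strongest reply is that the trial is randomised. The arms differ only by BMS-986253 in these 8 weeks, Study Endpoints compares secondary outcomes between arms, and randomisation balances natural growth on average. This stands. A reader might infer that the measure cannot separate any drug effect from the natural course; the documents do not support that. The limit applies within an arm, and so to nivolumab or to immunotherapy as a whole. For B versus A, what remains is a loss of precision.

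A reader might also infer that a PSA rise will be taken as absence of activity. The plan does not say so: it sets no threshold, within-arm test or decision rule for this outcome. Natural growth pushes the figure upward, so it cannot by itself produce a false fall, and a clear fall would still be visible.

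A third tempting reading is that the monthly tolerance, "PSA and serum testosterone will be checked monthly during treatment (+/- 3 days"), lets the week-8 sample fall after degarelix. The objective itself already requires the second PSA to precede ADT, and that specific definition governs the general window.

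It is also fair to say that subtracting an expected change based on each man's earlier slope could mislead. Men chosen because PSA is rising tend to have overstated prior slopes, so growth could appear to slow with no drug effect. This stands, and it is why the within-arm comparison should be descriptive.

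Finally, the size rests on assumed doubling times. The eligibility criteria and detailed study calendar are not in the public text read here. They may narrow the range or already require a PSA history, but the analysis text that is available does not use one.

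**Conclusion.** The point holds for the within-arm reading of a secondary objective. With no drug effect, the reported change would be about +11% to +53% for doubling times of 12 to 3 months. A true halving of growth would still appear as +5.5% to +23.7%. These figures assume exponential growth and doubling times that the documents do not supply.

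The B-versus-A difference is unbiased for the contribution of BMS-986253 but is silent on nivolumab, which both arms receive. Adjusting for growth rate offers a precision gain that is real but probably modest. The primary endpoint, its sample size and the safety objective are unaffected. This is an inexpensive improvement in analysis and interpretation, and it does not call the design into question.

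**What to change.** 1. Record the dated pre-study PSA values that showed each man's PSA was rising, if they are not already collected.
2. In Study Endpoints, name the 8-week PSA change and define it on the log scale. Replace the generic t-test for this outcome with a between-arm comparison adjusted for baseline log PSA and pre-study log-PSA slope.
3. Report each arm's 8-week change beside its pre-study slope as descriptive only. State that selection on a rising PSA can overstate the prior slope and so make growth appear to slow.
4. State that the raw percent change alone does not measure immunotherapy activity, and that the between-arm result addresses BMS-986253 only.

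The cost is a small amount of chart abstraction and revised analysis wording, with no new visit or sample. The slope covariate will be noisy when it rests on few values, which limits the precision gained but does not bias the randomised comparison.
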